## 4.0 PATIENT SELECTION / ELIGIBILITY CRITERIA

### 4.1 Inclusion Criteria

- 4.1.1 Diagnosis of an **advanced** solid tumor, lymphoma, chronic lymphocytic leukemia (CLL), or myeloma (no time restrictions or limitations) –**OR**– diagnosis of **early** stage solid tumor cancer, lymphoma, chronic lymphocytic leukemia (CLL), or myeloma  $\leq$  12 months prior to study enrollment.
- 4.1.2 Diagnosis of VTE  $\leq$  30 days prior to study enrollment for which potential benefits of anticoagulation therapy to prevent recurrence of VTE are felt by the treating physician to exceed the potential harms. Diagnosis may be made based on physical exam or imaging studies. Participants with both symptomatic and asymptomatic VTEs are eligible.  
Any anticoagulation drug/strategy may be used to treat the index VTE; protocol treatment will begin  $\leq$  14 days after enrollment.
- 4.1.3 Treating physician *intends* to put participant on anticoagulation therapy for at least three months.
- 4.1.4 Age  $\geq$  18 years.
- 4.1.5 Platelet count is  $\geq$  50,000/mm^3 ( $\leq$  7 days prior to enrollment).
- 4.1.6 CrCl (Creatinine Clearance) is  $\geq$  15 ml/min ( $\leq$  7 days prior to enrollment).

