#### 11.5 Dose Modifications

Dose modifications are allowed, and are not considered protocol violations.

- Skipped or omitted doses are not protocol violations.
- Drug discontinuation is not a protocol violation.
- Delayed or postponed doses are not protocol violations.
- Dose reductions are not protocol violations and should be done at the discretion of the treating clinician.
- Re-escalation of doses is not a protocol violation and should be done at the discretion of the treating clinician.

***When making dose modifications, the guiding principal should be:*** Regardless of treatment arm and/or anticoagulation drug(s) used, treat the patient according to individual institutional guidelines, the best clinical judgment of the responsible physician, and in consultation with the drug's package insert and with national treatment guidelines.

At 3 and 6 months, participants will report their use of treatment, the number of days with no anticoagulant therapy, and the number of days with each type of anticoagulant therapy. Study CRAs will also abstract this information from medical records at 6 months.

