### 3.5. Primary endpoint evaluation

#### 3.5.1. Primary endpoint

The primary endpoint is cumulative VTE recurrence reported by either patients or their clinicians at 6 months. A recurrent VTE is synonymous with the cumulative incidence of any VTE irrespective of the anatomic site. Note that we will analyze the VTE recurrent event rate at 6 months but the data we will use to assess this primary endpoint is not a dichotomous variable that indicates the presence/absence of cumulative VTE recurrent events at 6 months. The analysis variable we will use for the primary endpoint is time from enrollment to occurrence of a VTE recurrent event. We will estimate the VTE recurrent event at 6 months using a time-to-event analysis with this analysis variable, where deaths are handled as competing risks and lost-to-followup patients are handled as censored observations (see Section 3.5.2.1 for details). This approach accounts for censored observations more appropriately than an analysis using a dichotomous variable, whereas it yields the same result if there are no censored observations.

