#### 3.5.2. Analysis for the primary endpoint

##### 3.5.2.1. Primary analysis

The primary aim of this study is to compare the intervention and comparator arms with respect to their ability to prevent recurrent VTE. Because the intervention (DOAC therapy) is more easily administered than the comparator (usual care with LMWH warfarin), DOAC is expected to have higher adherence and therefore decreased incidence of VTE. Accordingly, a noninferiority design with a superiority alternative is preferred, as described by Friedlen et al. The primary analysis will test the noninferiority of the DOAC therapy with the primary analytic cohort (modified ITT population of the randomized cohort). If noninferiority is demonstrated, superiority of the DOAC therapy will be tested.

Because VTE is often a proximate cause of death in cancer patients' unexplained sudden demise, but diagnostic procedures are rarely performed (post-mortem scans, autopsies, etc.), we considered VTEs that were clinically significant as the primary outcome on the basis of an antemortem diagnosis. Separately, we looked at all-cause deaths because deaths from cancer and deaths from VTE are difficult to distinguish. Cancer patients routinely die at home and it is not possible to determine whether the proximate cause of death was a VTE, progression of tumor or some other cause. Indeed, the cause of many deaths in cancer patients is multifactorial. We will estimate the cumulative incidence of recurrent VTE at 6 months using standard competing risk analysis methods, where death will be treated as a competing risk. We calculate the difference in the 6 months incidence rate between groups and the corresponding 0.90 confidence interval (CI).

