#### 1) Noninferiority test of DOAC

The hypothesis for testing the noninferiority of the DOAC strategy is that the difference in the primary endpoint at 6 months is no greater than a noninferiority margin of 3% for the intervention-comparator. This noninferiority margin was selected based on what is acceptable to patients based on patient-stakeholder input as well as on input provided by clinicians

To confirm the noninferiority hypothesis, we will construct a two-sided 90% confidence interval (CI) for the difference in the cumulative incidence of the primary endpoint at 6 months (180 days). If the upper bound of the CI is less than 3%, we will conclude that the DOAC management strategy is non-inferior to the LMWH/warfarin strategy for management of VTE in patients with cancer.

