### 3.6.2. Analyses for secondary endpoints

- 1) *Cumulative rates of major bleeding reported by patients or clinicians at 6 months (grade 3, 4, or 5)*

We will repeat the analogous analyses as performed for the primary endpoint (see 3.5.2). The primary analysis plan for major bleeding, fatal or non-fatal, is also based on the sequential evaluation of noninferiority and superiority. We will construct a two-sided 90% CI for the difference in the cumulative incidence rate for the composite outcomes of major bleeding and death. If the upper bound of the CI is less than 2.5%, we will conclude that DOAC is noninferior to LMWH/warfarin in terms of major bleeding. The same secondary analyses as planned for the primary endpoint will be performed. In contrast to clotting, fatal bleeding events are usually clinically manifest and recorded and therefore can be distinguished.

- 2) *Cumulative incidence of all bleeding events reported by patients or clinicians at 6 months in the following categories: 1) major bleeding (Grade >=3), 2) clinically significant non-major (Grade 2); and, 3) nuisance bleeding (Grade 1)*

Clinically significant non-major bleeding is defined as Grade 2 Nuisance bleeding is defined as Grade 1 according to the NCI CTCAE criteria. We will perform the same analyses as described for major bleeding.

- 3) *Mortality*

Time from randomization to death from any cause is a secondary endpoint. The study is powered to confirm the primary hypothesis for recurrent VTE; we do not anticipate enough power to perform a confirmatory analysis for all-cause mortality. We will instead focus on providing quantitative information for the between-group difference for this endpoint. We will describe the survival time distribution by treatment group using the Kaplan-Meier method. Also, we will compare the restricted mean survival times (RMST) between groups. The truncation time point for calculating the RMST will be 6 months, which will give us an estimate of 6-month lifetime expectancy for each group. We will estimate the difference in RMST and the corresponding 90% CI. The hazard ratio for death and its 90% CI will also be calculated if the proportional hazards assumption is reasonable. The determination of the violation of the proportional hazards assumption will be based on a significant p-value (<0.05) for the Grambsch and Therneau test.

- 4) *The Patient-Centered Experience of Anticoagulation QOL and Burdens*

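### Major bleeding is held against the 2.5-point margin over the full 180 days, on drug or off, and no companion on-treatment analysis separates toxicity from length of exposure

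*Combined protocol and SAP*

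**What the plan says.** SAP 3.6.2(1), repeated in protocol 13.3.5(1), applies the primary-endpoint methods to major bleeding and sets the decision rule: "If the upper bound of the CI is less than 2.5%, we will conclude that DOAC is noninferior to LMWH/warfarin". Under SAP 3.5.1 the analysis variable for the primary endpoint is "time from enrollment to occurrence of a VTE recurrent event"; death is a competing event and loss to follow-up is censored. SAP 3.5.2.1 fixes six months at 180 days. That figure is stated for VTE and reaches bleeding through the carry-over. Neither section has a rule for stopping or switching drug.

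Time off drug is expected within that window:
- Protocol 4.1.3 requires only that the physician intends "to put participant on anticoagulation therapy for at least three months".
- Protocol 8.5 and 11.5 say that breaks, discontinuation and switching to the other arm's drugs are not violations.
- Protocol 7.0 (note on questionnaires and diaries) continues data collection to month 6 regardless of how long drug was taken.
- SAP 3.9.4 lists persistence subgroups down to 50% of days or fewer.

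Exposure is recorded. At 3 and 6 months patients report "the number of days with no anticoagulant therapy, and the number of days with each type of anticoagulant therapy" (protocol 11.5), and site staff abstract the same from the chart.

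On relative persistence, SAP 3.5.2.1 says "DOAC is expected to have higher adherence and therefore decreased incidence of VTE".

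The interval in the bleeding passage is described as being for the "difference in the cumulative incidence rate for the composite outcomes of major bleeding and death", although the conclusion drawn is about major bleeding.

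**The concern.** Anticoagulant bleeding is mainly a harm of being on the drug. A difference taken over a fixed calendar window, with off-drug days counted as follow-up, combines the bleeding risk while taking the drug with how long it was taken. Objective 2 concerns the harms of the two therapies, and SAP 3.8.1 names major bleeding as the primary protocol safety endpoint. A clinician advising a patient who will stay on treatment needs the first component, and the plan reports only the combination against the margin.

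SAP 3.2 shows that the authors were alert to this kind of problem. It adopts the modified ITT population so as to be conservative about noninferiority. That change deals with patients who never received the assigned strategy, but not with time after the drug is stopped or switched.

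**Working it through.** **1. Does any planned analysis remove off-drug time?**
- Modified ITT (SAP 3.2): at least one dose of the assigned strategy. All later days stay in.
- Safety: identical to modified ITT.
- ITT: everyone as assigned. All days stay in.
- Per-protocol: received the assigned drug with no major violation. Stopping and switching are not violations, so all days stay in.
- Persistence subgroups (SAP 3.9.4): exploratory, defined by behaviour after randomization, and not tied to the 2.5-point decision.
- Persistence rates (SAP 3.7): listed as separate endpoints, not linked to bleeding.

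So no bleeding analysis tied to the margin is limited to time on drug.

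**2. How much could it matter?** The documents state no bleeding rate, persistence or bleeding power, so there is no plan figure to reproduce.

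From the documents: margin 2.5 points; 90% two-sided interval (z = 1.645); 671 randomized 1:1, or about 335 per arm. The modified ITT set will be smaller by an amount not given.

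Assumed: control on-drug 180-day risk r_c of 3% or 5%; DOAC on-drug risk r_t = r_c + 2.5 points; constant hazards; fraction e of days on drug; off-drug hazard 0 or 25% of the control on-drug hazard (k = 0 or 0.25).

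Formulas, for major bleeding alone:
- λ = −ln(1 − r)
- risk over 180 days: p = 1 − exp(−λe − kλ_c(1 − e))
- d = p_t − p_c; SE = √{[p_c(1 − p_c) + p_t(1 − p_t)]/335}
- P(noninferior) = Φ((0.025 − d)/SE − 1.645)

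Worked line, r_c = 5%, e = 0.8 in both arms, k = 0: p_c = 1 − 0.95^0.8 = 4.02%; p_t = 1 − 0.925^0.8 = 6.05%; d = 2.03 points; SE = 1.69 points; P = Φ(0.281 − 1.645) = 8.6%.

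| Days on drug, control / DOAC | k | d, r_c = 3% | P | d, r_c = 5% | P |
|---|---|---|---|---|---|
| 100% / 100% | – | 2.50 | 5.0% | 2.50 | 5.0% |
| 80% / 80% | 0 | 2.02 | 9.7% | 2.03 | 8.6% |
| 80% / 80% | 0.25 | 2.01 | 9.6% | 2.02 | 8.6% |
| 60% / 60% | 0 | 1.53 | 19.8% | 1.54 | 16.0% |
| 60% / 60% | 0.25 | 1.52 | 18.8% | 1.53 | 15.2% |
| 60% / 80% | 0 | 2.61 | 4.2% | 3.02 | 2.5% |
| 60% / 80% | 0.25 | 2.46 | 5.3% | 2.76 | 3.6% |

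Equal persistence dilutes the excess. Better DOAC persistence offsets or reverses the dilution.

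**3. Different stopping pattern.** With exponential discontinuation, 334 per arm and off-drug hazard 0 or 30% of control, equal stopping of 20-50% by day 180 gives 2.25 down to 1.81 points (P about 7-13%). With 20-30% stopping on DOAC against 50% on control, the difference is 2.36-3.11 points (P about 2-6%). The pattern is the same, with less dilution.

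**4. The composite wording.** If the tested quantity really is bleeding or death, the table does not describe it. At an assumed composite risk of 15-30% in both arms and 334 per arm, SE = √[2p(1 − p)/334] = 2.76 to 3.55 points. The 90% half-width is 4.5 to 5.8 points, and P(noninferior) with equal arms is only 0.23 down to 0.17.

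**The case against.** The strongest reply is that this is a pragmatic effectiveness trial comparing strategies, and its stated objective is the cumulative rate of major bleeding at six months. If the 180-day difference truly is 1.5 points, it lies inside the margin and noninferiority is the correct conclusion for the strategy. This stands. A reader might take the 9-20% in the table as an inflated type I error of the planned test. It is not: those figures measure the 180-day test against an on-drug margin that the plan never claims.

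A reader might also infer that time off drug necessarily makes noninferiority easier to show. The documents do not support that. It needs equal or worse persistence on DOAC, whereas the plan expects better adherence there, and the calculation then gives P of 2.5-5.3%, around or below the nominal 5%.

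Two further replies stand in part. The persistence subgroups are to receive the same analyses, bleeding included, so exposure is not ignored; but those groups form after randomization and cannot isolate on-drug risk. The three-month intention is a minimum, and protocol 11.1 runs protocol treatment to six months; but discontinuation and gaps are explicitly allowed within it.

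Finally, on-treatment censoring has its own bias. Patients stop for reasons related to bleeding risk, and protocol 11.4 has drug interrupted around invasive procedures. This is why such an analysis should be supportive and not a second condition for the noninferiority claim.

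**Conclusion.** The point holds as a gap in the supporting analyses, not as an error in the main one. The 180-day comparison is valid for the strategy, but it mixes toxicity with exposure, and nothing tied to the 2.5-point rule separates them. Under the assumed rates, an on-drug excess equal to the margin appears as about 1.5-2.0 points with equal persistence of 60-80%, or about 2.5-3.0 points with 80% of days on DOAC against 60% on control. The direction depends on persistence by arm, which the documents do not quantify. The sizes rest on assumed bleeding risks, constant hazards and the full randomized cohort, and they apply to major bleeding alone. A companion analysis is a cheap improvement. The composite wording is a separate inconsistency in the same passage and needs to be resolved in any case.

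**What to change.** In SAP 3.6.2(1) and protocol 13.3.5(1):

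- Keep the 180-day comparison as the main analysis, and word its conclusion as applying to the 180-day strategy.
- Add a prespecified supportive on-treatment analysis of major bleeding, from first dose of the assigned strategy to permanent stop or switch plus a fixed analysis window. Thirty days would match the expedited-reporting period in protocol 12.1.
- Report it against the same 2.5-point reference, beside time on drug by arm. Use inverse-probability censoring weights as a check, because stopping can be informative. Do not make its upper bound a second gate.
- Reconcile the bleeding-and-death composite with the major-bleeding conclusion, so that one quantity is tested and named.

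The cost is SAP wording and one more analysis. Protocol 8.7 and 11.4 place treatment given, breaks and medication history on the Medical Record Abstraction Form, with monthly diaries alongside. The documents do not say that exact stop and switch dates are captured, and missing diaries are not violations (protocol 7.0), so completeness of the exposure data should be checked before the analysis is specified. The on-treatment interval may be wider. No treatment rule changes.

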## 4.2.7 Pregnant or nursing.

**4.3 Definitions and answers to FAQs with regard to the eligibility criteria**General:

- Non-English speaking participants are eligible for participation in this study. Sites must follow their local SOPs for consenting non-English speaking participants. Translated materials are currently available in Spanish.

Criterion 4.1.1:

- “Advanced” cancer means stage IV, metastatic, and/or recurrent cancer.
- If diagnosed with advanced cancer, then date of cancer diagnosis can be any date (no time restrictions or limitations).
- “Early stage” cancer means any cancer EXCEPT one that is stage IV, metastatic, and/or recurrent.
- If diagnosed with early stage cancer, then the diagnosis date must be  $\leq$  12 months prior to the date on which the patient is enrolled on this trial.
- Patients with multiple malignancies are eligible as long as other criteria are met.
- DCIS (ductal carcinoma in situ) and MDS (myelodysplastic syndromes) are not eligible.
- Primary CNS (central nervous system) tumors, primary brain tumors, and/or brain metastases are eligible.

Criterion 4.1.2:

- Patients with a history of prior VTE and prior anticoagulation are allowed.
- “VTE” means PE, DVT, and/or portal vein thrombosis (any or all are acceptable).
- **VTE stands for Venous Thromboembolism.** A VTE is a blood clot that breaks loose and travels in the blood. DVTs and PEs are types of VTEs.
- **PE stands for Pulmonary Embolism.** A PE is a sudden blockage in a lung artery (often caused by a DVT that breaks loose and travels through the bloodstream to the lung).
- **DVT stands for Deep Vein Thrombosis.** A DVT is a blood clot that forms in a vein deep in the body, often in the leg or pelvis.
- The following types of VTE are also eligible: any line associated clot, calf vein, splanchnic, and sub-segmental PE are eligible. It is recommended that sites not enroll superficial vein thrombosis unless there is intention to treat with full dose anticoagulation for at least 3 months.
- The VTE diagnosis that makes a patient eligible for this study will be referred to as the “**index VTE**” throughout this protocol.
- **“Recurrent VTE”** is defined as the emergence of venous thrombosis of a site that was either previously uninvolved or had interval documentation of incident DVT or PE resolution.

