#### 2) *Cumulative incidence of all bleeding events reported by patients or clinicians at 6 months in the following categories: 1) major bleeding (Grade $\geq 3$ ), 2) clinically significant non-major (Grade 2); and, 3) nuisance bleeding (Grade 1)*

Clinically significant non-major bleeding is defined as Grade 2 Nuisance bleeding is defined as Grade 1 according to the NCI CTCAE criteria. We will perform the same analysis as described above for major bleeding events.

*3) Mortality (Cumulative incidence of death at 6 months)*

Time from randomization to death from any cause is a secondary endpoint. The study is powered to confirm the primary hypothesis for recurrent VTE; we do not anticipate enough power to perform a confirmatory analysis for all-cause mortality. We will instead focus on providing quantitative information for the between-group difference for this endpoint. We will describe the survival time distribution by treatment group using the Kaplan-Meier method. Also, we will compare the restricted mean survival times (RMST) between groups. The truncation time point for calculating the RMST will be 6 months, which will give us an estimate of 6-month lifetime expectancy for each group. We will estimate the difference in RMST and corresponding 90% CI. Hazard ratio and its 90% CI will also be calculated if the proportional hazards assumption is reasonable. The determination of the violation of the proportional hazards assumption will be based on a significant p-value (<0.05) for the Grambsch and Therneau test.

*4) The Patient-Centered Experience of Anticoagulation QOL and Burdens*

*a. Health Related Quality of Life (SF-12) at 3 and 6 months*

For SF-12, the primary analysis variable is the difference in the SF-12 mean change score from baseline. We will consider 2-point differences as clinically meaningful. We will use multiple imputations to handle missing observations.

First, we will create 10 complete datasets, imputing missing values using chained equations, where we include measurements at baseline, 3 months, and 6 months. Second, we will estimate mean changes and the standard errors for each of the 10 complete sets. We will then use Rubin's method to derive an estimate for the difference in the mean change score between two groups. Using the resulting estimate and the standard error, we will perform a Z-test to evaluate equality of SF-12 scores between groups.

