### 4) Analysis by type of VTE recurrence

We will also conduct the same analyses for each of the following subtypes of VTE recurrence.

- 1) Pulmonary embolism (PE) with or without deep vein thrombosis (DVT)
- 2) DVT without PE

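### The plan gives all, grade 2 and grade 1 bleeding the same analyses as major bleeding, which read literally carries over a 2.5-point noninferiority test and a composite with death that are not justified for those outcomes

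*Combined protocol and SAP*

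**What the plan says.** SAP 3.6.2(1) sets out the plan for major bleeding (grades 3 to 5). It "is also based on the sequential evaluation of noninferiority and superiority". It calls for a two-sided 90% CI for "the difference in the cumulative incidence rate for the composite outcomes of major bleeding and death" and gives a decision rule: "If the upper bound of the CI is less than 2.5%, we will conclude that DOAC is noninferior to LMWH/warfarin in terms of major bleeding".

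SAP 3.6.2(2) then covers all bleeding and the grade 2 and grade 1 categories. Apart from defining the grades, its analysis is one sentence: "We will perform the same analyses as described for major bleeding". Protocol 13.3.5(2) has the equivalent: "We will perform the same analysis as described above for major bleeding events". SAP 3.8.2 also sends any bleeding to section 3.6.2.

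For VTE subtypes, SAP 3.5.2.3(4) and protocol 13.3.3(4) say: "We will also conduct the same analyses for each of the following subtypes of VTE recurrence". The subtypes are PE with or without DVT, and DVT without PE. The primary analysis in SAP 3.5.2.1 is a noninferiority test at 3 points, followed by superiority.

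No other margin is given for any of these outcomes, and none is labelled as estimation only. Elsewhere the SAP does use such labels. Mortality in 3.6.2(3) is to be described quantitatively rather than confirmed, and the subgroup analyses in 3.9 are called exploratory.

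**The concern.** A noninferiority margin states how much extra risk is acceptable for one particular outcome. The SAP bases the 3 points for recurrent VTE on patient and clinician input. It gives no basis for the 2.5 points for major bleeding. Neither document argues that a tolerance for grade 3 to 5 bleeding also suits nuisance bleeding, or that a tolerance for all recurrent VTE also suits PE.

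If the cross-reference is followed, an outcome much more frequent than major bleeding will usually end as noninferiority not shown, even when the drugs do not differ. For a rare VTE subtype, a large relative increase can fall inside the margin. The literal reading also turns grade 1 bleeding into grade 1 bleeding or death, which is hard to interpret. If the cross-reference is not followed, these outcomes have no stated decision rule, and whether to announce noninferiority could be settled after the results are seen.

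**Working it through.** **Inputs from the documents**
- 671 randomized, 1:1 (SAP 2.4 and 2.5), so 335.5 per arm. The modified ITT size is not stated and would be smaller.
- Two-sided 90% CI for VTE and bleeding (SAP 3.1), so z = 1.645. The primary endpoint has a final critical value of 1.710 (SAP 3.5.2.2).
- Margins of 2.5 points (SAP 3.6.2) and 3 points (SAP 3.5.2.1).

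**Assumed:** the event rates. The documents give no expected rate for these bleeding categories or VTE subtypes.

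**Formula** (p_T for DOAC, p_C for control, n per arm)

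SE = √[p_T(1−p_T)/n + p_C(1−p_C)/n]

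P(pass) = Φ[(margin − (p_T − p_C))/SE − 1.645]

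**Check against the plan's own table.** The power table in SAP 2.5 does not state its event rates, so 0.900 cannot be rebuilt from inputs. The step from 668 to 750 randomized can be checked by scaling with √(750/668) = 1.0596:
- Noninferiority: Φ[(1.2816 + 1.645) × 1.0596 − 1.645] = 0.927 (stated 0.927).
- Superiority: about 0.798 (stated 0.797).
- CI length: 6.1/1.0596 = 5.76 points (stated 5.8).

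The formula therefore behaves as the plan's own calculation does. The table gives no power for the outcomes at issue here.

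**2.5-point margin, identical drugs.** Example at 10%: SE = √(2 × 0.10 × 0.90/335.5) = 2.32 points; P = Φ(2.5/2.32 − 1.645) = 0.286.

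| Assumed rate | CI half-width (points) | P(pass) | Risk ratio at the margin |
|---|---|---|---|
| 1% | 1.26 | 0.946 | 3.5 |
| 5% | 2.77 | 0.437 | 1.5 |
| 10% | 3.81 | 0.286 | 1.25 |
| 20% | 5.08 | 0.202 | 1.125 |
| 30% | 5.82 | 0.174 | 1.08 |

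Exact binomial sums at 335 per arm give 0.289, 0.203 and 0.174 for the last three rows. From 5% upward the half-width exceeds the margin, so an observed difference of zero fails. At a 20% control rate, the observed DOAC rate must be about 17.5% or lower to pass.

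The nearest rates in the documents are the bleeding columns of protocol Table 2, from general VTE trials with few cancer patients. Across their range of 1.2% to 11.4%, P(pass) with identical drugs falls from 0.908 to 0.266.

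**If the composite with death also carries over**, the base rate rises. At assumed composite rates of 15% to 35%, identical drugs pass with probability 0.230 down to 0.167.

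**3-point margin on a VTE subtype**

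| Assumed control rate | P(pass), identical drugs | P(pass), risk doubled | Risk ratio at the margin |
|---|---|---|---|
| 1% | 0.988 | 0.687 | 4.0 |
| 2% | 0.871 | 0.188 | 2.5 |
| 3% | 0.737 | 0.050 | 2.0 |

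Using 1.710 instead of 1.645 changes little (0.986 rather than 0.988 in the first row).

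**How far the drug still decides.** At a 20% bleeding rate and 2.5 points, P(pass) is 0.982 at a risk ratio of 0.6, 0.709 at 0.8, 0.202 at 1.0 and 0.008 at 1.25. When the true difference equals the margin, P(pass) is 0.05 at every base rate by the formula (0.050 to 0.066 by exact sums at rates of 1% or more).

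**The case against.** **The carry-over is inferred.** No sentence states a margin for the milder bleeding categories or the VTE subtypes. The 2.5% conclusion is worded for major bleeding, and the 3% margin for the primary endpoint. This stands, so the defect is a cross-reference that imports too much when read literally, not an explicit rule. For bleeding the literal reading is still the natural one, because the sequential test is the main thing described for major bleeding.

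**The VTE half is weaker.** SAP 3.5.2.3(4) sits among secondary analyses of the primary endpoint, and items 1 to 3 there are estimates with 90% CIs. The wording could refer only to those. Where the plan wants a noninferiority gate elsewhere, as for highly thrombogenic tumors in SAP 3.9.1, it says so. This also stands.

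**Low power is not a false claim.** Noninferiority not shown does not mean harm. A PE rate of 2% against 3% is a 1-point difference, inside a 3-point absolute margin, so calling it noninferior would be correct under that margin. The fair complaint is that the margin is unjustified for the subtype.

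Two stronger readings are tempting and not supported:
- A reader might infer that verdicts would follow the base rate rather than the drug. The figures above show that both matter and that error at the margin stays near 5%.
- A reader might infer that the two VTE subtypes leave out other-site recurrences, because protocol 4.3 says VTE "means PE, DVT, and/or portal vein thrombosis (any or all are acceptable". That line explains eligibility for the index event. The same section defines DVT as a clot in a deep vein, often but not only in the leg or pelvis, and SAP 3.4 codes clot type as PE, DVT, both or unknown. Nothing shows that other-site recurrences are excluded from DVT without PE, and the plan does not say that the subtypes must sum to the total.

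**Conclusion.** The point holds for bleeding as a defect of specification with a practical consequence, and less firmly for the VTE subtypes. Followed literally, the plan tests all, grade 2 and grade 1 bleeding against a margin set for major bleeding, on a composite with death. At assumed rates of 10% to 30%, identical drugs would then fail to show noninferiority about 71% to 83% of the time. If the 3-point margin is carried to a VTE subtype with an assumed 1% rate, it tolerates a risk ratio of up to 4, and a drug that doubles the risk passes about 69% of the time.

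These sizes rest on assumed event rates and on all 671 randomized patients. In the smaller modified ITT population the pass probabilities quoted here for identical drugs, and for a doubling at 1%, would be lower. The primary noninferiority test is not affected.

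**What to change.** Add a sentence to SAP 3.6.2(2) and 3.5.2.3(4), and to protocol 13.3.5(2) and 13.3.3(4), to this effect:
- In the randomized cohort as a whole, noninferiority and superiority conclusions are drawn only for the primary endpoint and for major bleeding.
- All, grade 2 and grade 1 bleeding and the two VTE subtypes are reported as 6-month differences in cumulative incidence and subhazard ratios, with 90% CIs and no verdict.
- Death is handled as a competing risk for these outcomes, not as part of a grade 1 or grade 2 bleeding composite.

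If a verdict is wanted for any of them, it needs its own margin with a stated reason.

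The cost is wording and the loss of formal tests on these secondary outcomes. No data are lost, and the Fine and Gray model and the competing-risk estimates are already planned for the primary endpoint. The tests of the primary endpoint and major bleeding, and the separate subgroup rule in SAP 3.9.1, need no change for this point.
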